- r) Subject is currently enrolled in a clinical study of any other investigational drug or device.
- s) Any other condition or laboratory value that would, in the professional opinion of the Investigator, potentially affect the subject's response or the integrity of the data or would pose an unacceptable risk to the subject.

2.8 ***Informed Consent***

Study candidates shall receive an explanation of the study objectives, possible risks and benefits of the study, and be given adequate time to read the information included in the informed consent document. Candidates will be given an opportunity to ask questions about any of the information contained in the informed consent. Candidates must verbally acknowledge understanding of the informed consent and sign the consent form accordingly. This form must have prior approval of the Institutional Review Board (IRB).

2.9 ***Screening Procedures***

Once informed consent is obtained, interested subjects will undergo screening.

Screening Visit; Required; Day -60 to Day 0

After the informed consent is signed, subjects will be screened to determine if all eligibility criteria are met. The Investigator or designee shall complete a brief medical history and examine the subject to confirm eligibility for the study.

1. Obtain height and weight.
2. Calculate BMI.
3. Assess for any medical conditions that would lead to exclusion of a subject from the study.
4. [REDACTED]
- [REDACTED]
- [REDACTED]
5. Document medication use, Fitzpatrick Skin Type, and ethnicity.
6. All female subjects of childbearing potential will be asked to take a pregnancy test (urine) prior to being treated. If the subject is pregnant, she will be excluded from participation.

Female subjects of childbearing potential will be advised to avoid becoming pregnant during the study by using a medically accepted form of contraception if they are sexually active. If the subject becomes pregnant during the study, she will not be treated subsequently with the study device or be required to have follow-up photographs taken or any other efficacy assessment performed.

All subjects will be asked to maintain their weight by not making any major changes to their diet or exercise regimen during the study. Subjects who do not maintain their weight within 5% will continue in the study. However, if the weight change is more than 5% after the final treatment, the subjects' data will be excluded from the per-protocol data analysis.

ZELTIQ P/N: [REDACTED]

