2.10 Enrollment

Study candidates who sign the informed consent form, meet eligibility criteria, and undergo initiation of study treatment are considered enrolled. Study treatment initiation is defined as the initiation of treatment with a study device after the placement of the applicator on the intended treatment area on the scheduled treatment day.

2.11 Photo Visit; Required, day -30 to 0

All subjects will have their photos taken within 30 days prior to first study treatment.

- a) Obtain weight.
- b) [REDACTED]
[REDACTED]
[REDACTED]
- c) Obtain baseline 2-Dimensional photographs of the treatment area using standardized setup and settings.

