2.12 Study Treatment

[REDACTED]
[REDACTED]
[REDACTED]

[REDACTED] The abdomen and/or buttocks may be treated. [REDACTED]
[REDACTED]
[REDACTED]
[REDACTED]

Treatment Visit 1

Prior to EMS Treatment

- a) Review and confirm subject meets all of the inclusion criteria and none of the exclusion criteria, then proceed with the study treatment.

ZELTIQ P/N: [REDACTED]
Protocol Number: ZA19-002

This document and the contents hereof are considered proprietary and confidential information of ZELTIQ Aesthetics, Inc. Disclosure to unauthorized individuals or dissemination, publication or copying is prohibited without prior written consent of ZELTIQ.

- b) Repeat pregnancy test for female subjects of childbearing potential (urine).
Exclude subject from participation if the results are positive.
- c) Obtain weight (Note: weight measurement is only required prior to first EMS treatment).
- d) Subject completes Body Satisfaction Scale for abdomen and or Body Satisfaction Scale for buttocks as appropriate. Note: Completion of these scales is required prior to first EMS treatment).

EMS Treatment Steps

- e) Apply EMS device per manufacturer's Instructions for Use.
- f) Support the EMS device with pillows or straps as needed.
- g) Initiate treatment using recommended program for toning and firming the targeted treatment area supplied by manufacturer.
- h) Record the highest percent (%) energy utilized for the EMS treatment.

[REDACTED]

[REDACTED]

[REDACTED]

Treatment Visits 2 and 3

The required study activities are the same for both Treatment Visits 2 and 3:

Prior to EMS Treatment

- a) Review and confirm subject meets all of the inclusion criteria and none of the exclusion criteria.
- b) Repeat pregnancy test for female subjects of childbearing potential (urine).
Exclude subject from participation if the results are positive.

EMS Treatment Steps

- c) Apply EMS device per manufacturer's Instructions for Use.
- d) Support the EMS device with pillows or straps as needed.
- e) Initiate treatment using recommended program for toning and firming the targeted treatment area supplied by manufacturer.
- f) Record the highest percent (%) energy utilized for the EMS treatment.

g) [REDACTED]
[REDACTED]
[REDACTED]

Treatment Visit 4

Prior to EMS Treatment

- a) Review and confirm subject meets all of the inclusion criteria and none of the exclusion criteria, then proceed with the study treatment.

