- b) Repeat pregnancy test for female subjects of childbearing potential (urine). Exclude subject from participation if the results are positive.

EMS Treatment Steps

- c) Apply EMS device per manufacturer's Instructions for Use.
- d) Support the EMS device with pillows or straps as needed.
- e) Initiate treatment using recommended program for toning and firming the targeted treatment area supplied by manufacturer.
- f) Record the highest percent (%) energy utilized for the EMS treatment.
- g) [REDACTED]
[REDACTED]
[REDACTED]

Post-EMS Treatment # 4

- h) Subject completes Body Satisfaction Scale(s) (for abdomen and/or buttocks, as appropriate)
- i) [REDACTED]
[REDACTED]
- j) Optional - Obtain 2-Dimensional photographs of the treatment area using standardized setup and settings.

The need for post-treatment care is not expected following the EMS treatments performed in this study. Subjects will be encouraged to call the study site if they experience any unusual effects (e.g., severe discomfort etc.), which may be related to the study.

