2.13 Follow-up Procedures

Subjects who receive study treatment are required to complete all follow-up visits and assessments (4-Week and 12-Week).

2.13.1 Four-Week Post-Final Treatment Visit; 4 Weeks \pm 1 week;

The following activities will be performed at the 4-week visit:

- a) Obtain weight.
- b) Assess for adverse events.
- [REDACTED]
- d) Obtain standard 2D imaging of treatment areas
- e) Subject Completes SGAIS questionnaire
- f) Subject completes Body Satisfaction Scale for abdomen and/or Body Satisfaction Scale for buttocks as appropriate.
- [REDACTED]

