2.13.2 Twelve-Week Post Final Treatment Visit; 12 Weeks \pm 2 weeks

The following activities will be performed at the 12-Week visit:

- a) Obtain weight.
- b) Assess for adverse events.
- [REDACTED]
- [REDACTED]
- d) Optional - Obtain standard 2D imaging of treatment areas
- e) Subject Completes SGAIS questionnaire
- f) Subject completes Body Satisfaction Scale for abdomen and/or Body Satisfaction Scale for buttocks as appropriate.
- [REDACTED]

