2.18 Adverse Events

Adverse events (AEs) will be assessed continuously throughout the study. An adverse event is defined as any untoward medical occurrence in a participant, regardless of whether the event is related to the device.

All AEs and device deficiencies will be recorded on the corresponding CRF for the subject.

Adverse Device Effect (AE)

Any sign, symptom, or disease in a study participant that occurs during the course of a clinical trial that is determined by the Investigator to have a causal relationship or possible causal relationship with the device under investigation.

Device Deficiencies

A device deficiency is defined in accordance with ISO 14155 as inadequacy of a medical device including issues with respect to its identity, quality, durability, reliability, safety, or performance. Device deficiencies include malfunctions, use errors, and inadequate labeling.

If a device deficiency occurs, the investigational site will document the event using the CRF. Device deficiencies will be documented throughout the study and appropriately managed and reported to regulatory authorities and IRBs as required by Federal regulations.

Serious Adverse Event (SAE)

Any untoward medical occurrence in a participant, regardless of whether the event is related to the device that:

- a. results in death;
- b. results in a life-threatening illness or injury;

The term life threatening in the definition of serious refers to an event in which the participant was at risk of death at the time of the event. It does not refer to an event, which hypothetically might have caused death, if it were more severe.

- c. results in a permanent impairment of a body structure or body function;
 - Impairment of body function means a substantial disruption of a person's ability to conduct normal life functions.
 - This definition is not intended to include experiences of relatively minor medical significance such as uncomplicated headache, nausea, vomiting, diarrhea, influenza, and accidental trauma (e.g., sprained ankle) which may interfere with or prevent everyday life functions but do not constitute a substantial impairment.
- d. requires in-patient hospitalization or prolongation of existing hospitalization;
 - In general, hospitalization signifies that the participant has been detained (usually involving at least an overnight stay) at the hospital or emergency ward for observation and/or treatment that would not have been appropriate in the physician's

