office or outpatient setting. Complications that occur during hospitalization are AEs. If a complication prolongs hospitalization or fulfills any other serious criteria, the event is serious. When in doubt as to whether hospitalization occurred or was necessary, the AE should be considered serious. Hospitalization for elective treatment of a pre-existing condition that did not worsen from baseline is not considered an AE.

- e. results in medical or surgical intervention to prevent impairment to body structure or function;
- f. results in fetal distress, fetal death, or a congenital abnormality/birth defect.

Time Period and Frequency for Collecting AE and SAE Information

All AEs and SAEs from the signing of the ICF until the follow-up visit will be collected at the time points specified in the schedule of activities, and as observed or reported spontaneously by study participants.

Medical occurrences that begin after signing of informed consent and before administration of study treatment will be recorded on the Medical History/Current Medical Conditions section of the CRF not the AE section.

Unanticipated Adverse Device Effect (UADE)

Any serious adverse effect on health and safety or any life-threatening problem or death caused by, or associated with a device, if that effect, problem, or death was not previously identified in nature, severity, or degree of incidence in the investigational plan or application, or any other unanticipated serious problem associated with a device that relates to the rights, safety, or welfare of participants.

The Investigator shall be responsible for determination of the causal relationship of all adverse events to the device and/or procedure. The Principal Investigator is responsible for monitoring the safety of the participants enrolled.

Reportable Incidents

Serious adverse events (SAEs) and unanticipated adverse device effects (UADEs) must be recorded and reported to the manufacturer of the study device and to the Sponsor or designee within 24 hours of knowledge of the event.

Sponsor Contact:

ZELTIQ P/N: [REDACTED]
Protocol Number: ZA19-002

[name]
Director, Clinical Trial Management
ZELTIQ Aesthetics, an Allergan affiliate
[name]
[name]

[REDACTED]
[REDACTED]

A full reporting of the event shall be provided within 10 working days of the event. The Sponsor is then responsible for notifying the IRB, as required.

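### The pregnancy-test line at Treatment Visits 2 to 4 excludes a subject already treated, which read literally conflicts with section 2.13 and does not match section 2.9

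*Combined protocol and SAP*

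**What the plan says.** All references are to the combined protocol and SAP.

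- **2.12 Study Treatment.** The pre-treatment steps at Visit 1 include a urine pregnancy test and, if it is positive, "Exclude subject from participation if the results are positive". The steps for Visits 2 and 3 use the same words, and so does Visit 4: "Repeat pregnancy test for female subjects of childbearing potential (urine). Exclude subject from participation if the results are positive".
- **2.10 Enrollment.** "Study candidates who sign the informed consent form, meet eligibility criteria, and undergo initiation of study treatment are considered enrolled".
- **2.9 Screening Procedures.** Two cases are separated. A woman found pregnant before treatment is excluded. For a pregnancy that arises once the study is under way, the rule is that "she will not be treated subsequently with the study device or be required to have follow-up photographs taken or any other efficacy assessment performed". This second rule does not mention AE visits.
- **2.13 Follow-up Procedures.** "Subjects who receive study treatment are required to complete all follow-up visits and assessments (4-Week and 12-Week", with no exception for pregnancy. The 4-week and 12-week lists each include the item "Assess for adverse events".
- **2.18 Adverse Events.** "Adverse events (AEs) will be assessed continuously throughout the study", and "All AEs and SAEs from the signing of the ICF until the follow-up visit will be collected at the time points specified".
- **2.16.2 and 2.16.3.** The As-Treated Population is all treated subjects. Subjects who do not complete treatment are left out of the efficacy analyses. The primary safety endpoint is the frequency of device-related AEs, including serious ones (SAEs), summarized descriptively.

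**The concern.** The Visit 1 sentence was written for a candidate who has received nothing and is not yet enrolled. At Visits 2 to 4 the same sentence acts on an enrolled, exposed subject, and excluding her from participation reads as ending her part in the study. Section 2.9 keeps that expression for pregnancy found before treatment and uses different, narrower words for pregnancy during the study. Section 2.12 therefore applies the pre-treatment wording to the during-treatment case.

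At stake is the follow-up part of the safety record for any such subject. Device-related AEs are a primary endpoint, and she remains a treated subject whichever reading is used. If her follow-up assessments are not done, any error is toward fewer recorded events. The protocol allows up to 20 sites, so sites could handle the same situation differently.

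**Working it through.** The plan gives no figure on this point, so the check is a comparison of text plus a count from the visit schedule.

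**1. Status of the subject.** Under 2.10, initiation of the first treatment completes enrollment. Anyone tested before treatment at Visit 2, 3 or 4 has had at least one treatment, so she is enrolled and belongs to the As-Treated Population.

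**2. What each section tells the site to do after a positive test at Visits 2 to 4.**

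| Section | Device treatment | Photographs and efficacy assessments | AE follow-up at weeks 4 and 12 |
|---|---|---|---|
| 2.12, read literally | ends | end | ends |
| 2.12, read as a gate to treatment | ends | not addressed | not addressed |
| 2.9, pregnancy during the study | ends | waived | not mentioned |
| 2.13 | not addressed | required | required |
| 2.18 | not addressed | not addressed | collection continues to follow-up |

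The last column holds the problem. The literal reading of 2.12 contradicts 2.13 and 2.18. The gate reading contradicts neither.

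**3. What differs between the readings.** The AE row of Table 2 has 6 marks: EMS treatments 1 to 4 (4 marks) and the 4-week and 12-week visits (2 marks), 4 + 2 = 6. AE marks at later treatment visits are tied to treatments that 2.9 also stops, so they do not separate the readings. The two follow-up assessments do: the literal reading loses 2 of 2, the gate reading 0 of 2.

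**4. Effect on the endpoint.** The plan does not name the population for the AE summary. If it is the As-Treated Population (my assumption), she stays in the denominator. An event would be missing from the numerator only if it was device-related, arose or persisted after the visit with the positive test, and was never reported spontaneously.

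**5. Effect on efficacy.** None under either reading. She has not completed treatment, and 2.16.2 already leaves such subjects out.

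**6. How many subjects.** The documents give no number. The test must turn positive in the Week 1 to 2 treatment window, after negative tests at screening and Visit 1, in a study of at most 200 men and women. Very few, possibly none, is the reasonable expectation.

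**The case against.** The strongest reply is that the protocol, read as a whole, already settles the matter. A waiver of photographs and efficacy assessments in 2.9 makes sense only if the subject stays in follow-up, and because it covers efficacy alone, safety assessment is left in place. Sections 2.13 and 2.18 point the same way. The 2.12 line sits among the steps before that day's treatment, beside the eligibility check, and can be read as a gate to treatment. Most of this stands, and it is why the point is minor. What remains is that the gate reading asks a site to set a specific visit instruction aside in favor of general rules and an inference. No visible pregnancy-specific text tells it to do so. Parts of 2.12 are redacted and consent pages were removed, so that last statement covers only the visible text.

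Four stronger readings are tempting, and the documents do not support them:

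- *The protocol cancels AE follow-up for these subjects.* It does not. The implied rule is that follow-up continues; only the literal 2.12 wording says otherwise.
- *Most safety information on such a subject would be lost, because most of the calendar time lies after the positive test.* Time is not events. The anticipated effects in 6.2 are largely local and temporary, and AEs are assessed at each treatment visit.
- *The 2.12 line specifically endangers capture of fetal outcomes, SAE criterion f in 2.18.* That criterion also applies to a pregnancy arising after Visit 4, which the 2.12 line never reaches. Birth outcomes would normally fall after the 12-week visit under any reading.
- *Sections 2.9 and 2.13 contradict each other on efficacy assessments.* The former is a specific exception to a general rule, and for these subjects it has no analytic effect.

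**Conclusion.** The inconsistency is real and minor. The Visit 1 wording is reused at Visits 2 to 4 for a treated, enrolled subject. Taken literally, it conflicts with 2.13 and departs from the 2.9 rule for pregnancy during the study. For each subject handled that way, both scheduled follow-up AE assessments would be dropped while she still counts as treated.

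The overall effect should be very small. Few subjects can meet the condition, the safety endpoint is summarized without a test or threshold, and efficacy is untouched. Subjects are encouraged to call the site, spontaneous reports are collected, and SAEs must be reported within 24 hours of knowledge, so the loss is partly mitigated. The conclusion assumes that at least some sites would follow the visit instruction as written, and that no redacted or removed text resolves it.

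**What to change.** Reconcile the pregnancy-test wording for Visits 2 to 4 in 2.12 with 2.9, 2.13 and 2.18, for example by replacing the repeated Visit 1 sentence with a cross-reference to the during-study rule in 2.9. The text should make explicit that the 2.12 line does not end the AE and SAE data collection already scheduled for treated subjects. What happens to treatment after a positive test is for the sponsor to settle; this point takes no position on it.

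The cost is a wording change in the Visit 2 to 4 steps. It adds no visits or procedures, because Table 2 already schedules the 4-week and 12-week AE assessments, and it leaves the analysis unchanged.

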2.13 Follow-up Procedures

Subjects who receive study treatment are required to complete all follow-up visits and assessments (4-Week and 12-Week).

2.13.1 Four-Week Post-Final Treatment Visit; 4 Weeks \pm 1 week;

The following activities will be performed at the 4-week visit:

- a) Obtain weight.
- b) Assess for adverse events.
- [REDACTED]
- d) Obtain standard 2D imaging of treatment areas
- e) Subject Completes SGAIS questionnaire
- f) Subject completes Body Satisfaction Scale for abdomen and/or Body Satisfaction Scale for buttocks as appropriate.
- [REDACTED]

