2.13.3 Optional Follow-Up Evaluations (up to 4 within study period)

The full evaluation is not required at optional follow-up visits; the extent of the assessment will be at the discretion of the Investigator.

Table 2 summarizes the study schedule and events at each visit.

Table 2. Schedule of Visits

	Screening (< 1hr)	Photo Visit (<1hr)	EMS Treatment #1 (<4hrs)	EMS Treatment #2 (<4hrs)	EMS Treatment #3 (<4hrs)	EMS Treatment #4 (<4hrs)	4-Wk Follow-Up (< 1 hr)	12-Wk Follow-Up (< 1 hr)	Optional Follow-Up**
Time Frame	Day -60 to 0	Day -30 to 1	Week 1 (Day0)	Week 1	Week 2	Week 2	Week 4 (\pm 1 weeks)	Week 12 (\pm 2 weeks)	Open
Informed Consent*	X								
Eligibility Criteria	X		X	X	X	X			
Medical History	X								
Height & BMI	X								
Weight	X	X	X				X	X	
3D Photos and/or tape measurements		X				X#	X	X#	
2D Photos		X				X#	X	X#	
EMS			X	X	X	X			
[REDACTED]			X	X	X	X	X	X	
AE Assessment			X	X	X	X	X	X	
BSQ*** per body area			X			X	X	X	
[REDACTED]							X	X	
Subject GAIS							X	X	

* Informed Consent to be signed by subject prior to the collection of any data or initiation of any study procedures.

** Investigator discretion as to timing and extent of follow-up assessment for optional visits.

*** BSQ (Body Satisfaction Questionnaire)

Optional

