2.14.1 Global Aesthetic Improvement Scale (GAIS-Subject)

At 4-Weeks post-final treatment, subjects will be asked to rate the improvement observed in the treated area(s) using the Global Aesthetic Improvement Scale:

- 3 = Very much improved
- 2 = Much improved
- 1 = Improved
- 0 = No change
- -1 = Worse
- -2 = Much worse
- -3 = Very much worse

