3.4 Sponsor Responsibilities

General Responsibilities:

As the Sponsor, ZELTIQ Aesthetics assumes overall responsibility for the conduct of the study. ZELTIQ Aesthetics assumes all responsibilities per 21 CFR 812 and other applicable regulations, and shall:

IRB approval: Ensure IRB approval for the investigation before shipping the device to any Investigator.

Investigators: Select Investigators qualified by training and experience, and providing them with the information they need to conduct the investigation properly (21 CFR 812.43). Obtain a signed Investigator Agreement (21 CFR 812.43(c)) from each participating Investigator. Study sites will be evaluated to ensure that they have an adequate patient base and can provide sufficient staff and documentation support to conduct the study properly.

Monitoring: Select monitors qualified by training and experience to monitoring the study (21 CFR 812.43), and ensure proper monitoring of the investigation (21 CFR 812.46).

Investigational devices: Provide devices only to qualified Investigators (21 CFR 812.43). No study site may receive shipment of study devices until the following documents are received by the Sponsor:

- Signed Investigator's Letter of Agreement
- Signed Clinical Site Agreement
- Investigator current curriculum vitae

Data Management and analysis: Ensure data collection, verification, analysis, records storage, etc. Sponsor will assist with presentation(s) and/or publication(s).

Training

Study Training: To ensure uniform data collection and protocol compliance, Sponsor personnel will provide an educational session to study site personnel as needed, which will cover the Investigational Plan, techniques for the identification of eligible subjects, data collection and form completion, and the device directions for use. The Investigator and study staff will be trained on the study devices and protocol, applicable regulations and requirements, and expectations of the study, enrollment expectations, subject selection, informed consent, required clinical data and record keeping, etc.

Investigational Device Use: Representatives of the Sponsor will train Investigators in use of the study device prior to study initiation. Sponsor representatives may be present at study procedures.

Site Monitoring

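### The order of the primary BSQ and the SGAIS at follow-up is not fixed, and the visit lists put the SGAIS improvement rating first

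*Combined protocol and SAP*

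**What the plan says.** Section 2.13.1 opens its list with "The following activities will be performed at the 4-week visit". The readable items are weight (a), adverse events (b), 2D imaging (d), then "Subject Completes SGAIS questionnaire" (e), then "Subject completes Body Satisfaction Scale for abdomen and/or Body Satisfaction Scale for buttocks as appropriate" (f). One item between b and d and one after f are redacted. Section 2.13.2 has the same e-then-f order at 12 weeks. The Body Satisfaction Scale named in these lists is taken here to be the BSQ of sections 2.14.2, 2.14.3 and 2.15.1.

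At baseline (section 2.12, Treatment Visit 1, item d) the instruction is "Subject completes Body Satisfaction Scale for abdomen and or Body Satisfaction Scale for buttocks as appropriate", with the note "Completion of these scales is required prior to first EMS treatment". The SGAIS is not given at that visit: Table 2 marks it only at the 4-week and 12-week visits.

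Section 2.14.1 describes the SGAIS as a rating of change: "subjects will be asked to rate the improvement observed in the treated area(s) using the Global Aesthetic Improvement Scale". The scale runs from 3 to -3, with a no-change grade and three grades of worsening.

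Section 2.15.1 makes the 4-week BSQ the primary efficacy endpoint. Section 2.16.3 analyses it by tabulated means and by difference and percentage change from baseline. Section 2.1 describes a non-randomized study, and no control arm appears.

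**The concern.** A before-and-after comparison relies on the instrument being given in the same way at both times. If the SGAIS comes first at 4 weeks, subjects answer the BSQ items just after committing themselves to a statement about how far the treated area has changed. At baseline they answer the same items with no such statement behind them. A subject may then answer the BSQ so as to agree with the rating just given.

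With a concurrent control arm assessed in the same order, an effect of this kind could largely cancel. Here there is none, so the effect would be added to the BSQ change and could not be told apart from an effect of the device. If instead each of up to 20 sites chooses its own order, the primary measure is taken inconsistently across sites. Neither problem can be put right after the data are collected.

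**Working it through.** **Step 1. Is an order stated?** The places that bear on it, side by side:

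| Place | What it shows | Does it fix the order? |
|---|---|---|
| 2.13.1 and 2.13.2 | SGAIS (e), then BSQ (f) | No. The lead-in says what is done, not in what sequence |
| 2.12, Treatment Visits 1 to 4 | The same lettering runs through activities before, during and after treatment | Suggests that letters are steps, but says nothing about SGAIS and BSQ |
| 2.14.1 to 2.14.3 | SGAIS described before BSQ | No. It is a catalogue of instruments |
| Table 2 | BSQ row above Subject GAIS row | No. See step 2 |

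**Step 2. Does Table 2 settle it?** The BSQ row stands below the EMS row, yet section 2.12 requires the baseline BSQ before the first EMS treatment. The rows therefore do not run in time order, and the BSQ standing above Subject GAIS does not show that it is given first.

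**Step 3. Do the two time points differ?** Baseline: BSQ with no SGAIS at the visit. Four weeks: BSQ and SGAIS at the same visit, SGAIS listed first. Under the listed order they differ in this respect. With the BSQ first, this difference disappears.

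**Step 4. How large a shift would matter?** The plan gives no SD, effect size, power or scoring rule for the BSQ, so there is no figure to reproduce. What follows is an illustration.

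Assumptions: ten items (2.14.2, 2.14.3) scored 1 to 5 and summed; SD of the change score 6 to 10; n = 200, the enrolment maximum in 2.6; an order effect of 0.1 point per item.

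- Shift in the total: 10 × 0.1 = 1.0 point.
- 95% half-width of the mean change: 1.96 × SD / √n. At n = 200: 1.96 × 6 / 14.14 = 0.83 and 1.96 × 10 / 14.14 = 1.39.
- At n = 100 (an assumed number for one body area): 1.96 × 6 / 10 = 1.18 and 1.96 × 10 / 10 = 1.96.

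The shift is about the size of the half-width at n = 200 and smaller than it at n = 100.

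**Step 5. The same shift as a false-positive rate.** Let d be the shift divided by the SD of change, with a true effect of zero. For a two-sided 0.05 paired z-test, the chance of a significant result is Φ(d√n − 1.96) + Φ(−d√n − 1.96). A shift of 1.0 point gives d = 1.0 / 10 = 0.10 to 1.0 / 6 = 0.17.

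- n = 200, d = 0.10: d√n = 1.41; Φ(−0.55) plus a negligible second term = 29%.
- n = 200, d = 0.17 (1/6): d√n = 2.36; Φ(0.40) = 65%.
- n = 100, d = 0.10: d√n = 1.00; Φ(−0.96) + Φ(−2.96) = 17%.

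Section 2.16.1 sets the 0.05 level for all tests, but section 2.16.3 names no test for the BSQ. These rates apply only if such a test is made.

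**The case against.** The strongest reply is that nothing declares the letters a running order. Where timing matters the protocol says so, as in the note on the baseline scales, and it says nothing of the kind about the SGAIS and the BSQ. This stands. A reader might infer that the 4-week BSQ is in fact taken after the SGAIS, but the documents support only that it may be. The reply does not remove the point, because silence leaves the order to each site and the one list a site would follow puts the SGAIS first.

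A reader might also infer that the order favours the device. The documents do not show this. The SGAIS offers no change and three grades of worsening, so carry-over could lower the BSQ in some subjects. An upward shift is plausible, because the question asks about improvement and subjects sought toning and know they were treated, but it is inference. The size is equally unknown: the 0.1 point per item, the SDs and the summed scoring are all assumed. The figure of 200 is a maximum, the BSQ is taken per body area, and the primary analysis uses the per-protocol set, so the numbers analysed may be smaller.

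Three further inferences go beyond the text:

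- **That only a few known steps precede either BSQ, or that subjects rate the SGAIS with no baseline picture.** Redacted items at the visits and in section 2.14 prevent either statement.
- **That sponsor staff may sit in on the questionnaires.** The sentence "Sponsor representatives may be present at study procedures" belongs to the paragraph on device use in section 3.4 and is not about questionnaires.
- **That no post-treatment BSQ is free of the SGAIS.** A BSQ is also completed after the fourth treatment, at a visit with no SGAIS. It is taken at a different time and cannot replace the 4-week primary score.

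Finally, the lack of a control arm is a limit of the design that reordering two forms does not cure. That is correct. Reordering removes one avoidable difference between the two measurements and no more.

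**Conclusion.** The point holds as a minor one. The plan does not fix the order of the BSQ and the SGAIS at follow-up, and its visit lists put the SGAIS first. Followed as written, they would have the primary 4-week score taken under a condition absent at baseline, and any resulting order effect would pass straight into the primary change.

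The finding rests on the readable text of sections 2.12, 2.13 and 2.16.3 and on Table 2. The size of any effect rests on assumptions alone. The illustration shows that a shift small on each item could be comparable with the precision of the mean change at full enrolment. It does not estimate a bias or show that one exists.

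**What to change.** In sections 2.13.1 and 2.13.2, list the BSQ before the SGAIS and add one sentence, for example: At every follow-up visit, at all sites, subjects complete the BSQ before the SGAIS. The same sentence covers optional visits where both are given.

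No change to Treatment Visit 1 is needed, since no SGAIS is given there. Moving the baseline BSQ to the start of that visit would place it ahead of the eligibility review and pregnancy test for no gain on this point.

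The cost is the relettering of two items in two lists and a mention in site training. No visit, procedure, form or staff time is added. The change has to be made before follow-up visits begin, because the order cannot be corrected afterwards.
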